12.6 Device Failures, Malfunctions and Nonconformities

All investigational device failures, malfunctions, and product nonconformities will be documented on the appropriate CRF and the involved device(s) should be returned to the Sponsor for analysis, if possible. Instructions for returning the investigational device(s) will be provided to the study sites in their Study binder. Device failures and malfunctions should also be documented in the subject's medical record. All investigational device failures, malfunctions, and product nonconformities shall be reported within 24 hours of becoming aware to the Sponsor.

All device malfunctions and nonconformities related to the interventional mechanical thrombectomy devices used in the procedure also should be reported in the CRFs.

13 Safety Monitoring

13.1 Data Safety Monitoring Board

An independent Data Safety Monitoring Board (DSMB) will review the safety data, including reportable adverse events. The DSMB will be empowered to recommend suspension of enrollment or termination of the study based on safety concerns. Based on their analysis, the DSMB may recommend that the sponsor modify or stop the study. Every effort will be made to allow the DSMB to complete an unbiased review of internal and external scientific factors relevant to the safety of the patient populations and the conduct of the study. The DSMB will be composed of a multi-disciplinary group of physicians and a statistician. The committee members will not be participating in the study and will not have an affiliation with the Sponsor, Investigators, Investigational sites, or core laboratories. Names of the members will not be announced but will be provided by the sponsor to the appropriate regulatory agencies upon request. The DSMB chairperson will notify the sponsor of any safety or compliance issues throughout the course of the study. The committee will also provide confidential recommendations, when necessary, of study termination based on safety stopping rules determined at the study onset, or because a clinically significant result or trend was identified in safety analyses of data. All DSMB reports will remain strictly confidential but will be made available to the appropriate regulatory agencies upon request.

During the course of the study, the DSMB will review accumulating safety data to monitor the incidence of Adverse Events and other trends that would warrant modification or termination of the study. The DSMB will meet at pre-specified intervals to assess the data against the prespecified safety and efficacy stopping rule as described within the DSMB Charter. In addition to the pre-specified meetings, the DSMB will meet for any other safety concerns that might arise during the active enrollment phase of the study. In addition, a designated member of the DSMB will be sent SAE data at regular time intervals, independent from the pre-planned DSMB meeting schedule. Data will be supplied to, and reviewed by, the DSMB as tables and/or listings. After review of the aggregate data, the DSMB may request additional information. The DSMB can also consider external data when appropriate, (e.g., published articles). Any DSMB recommendations for study modification or termination because of concerns over subject safety or issues relating to data monitoring or quality control will be submitted in writing to the Sponsor for consideration and final decision. However, if the DSMB at any time determines that a potential serious risk exists to subjects in this study, the DSMB chairman will immediately notify the Sponsor. The composition, guiding policies, operating procedures and stopping rules (if safety concerns arise during the review of the study data) will be described in the DSMB Charter.

13.2 Clinical Events Committee (CEC)

An independent Clinical Events Committee will be assembled to review and adjudicate all potential endpoint events and their relationship to the device or procedure that occur while a patient is enrolled in the trial. The committee will be comprised of a multidisciplinary group of physicians including at least one neurointerventionalist and at least one cardiologist. The committee members will not be participating in the trial and will not have an affiliation with the Sponsor, Investigators or Investigational sites. The composition, guiding policies and operating procedures will be described in the CEC Charter.

13.3 Core Lab

A central imaging core lab will be established to independently review angiographic and CTP imaging. Angiographic images will be reviewed to provide an independent assessment of the secondary efficacy endpoint of mTICI reperfusion scores at post procedure. CTP images obtained at baseline and at 24 (+/- 6) hours will be reviewed to determine volume of infarct and mismatch for DSMB assessment.

Instructions for standardized imaging and transfer will be provided to site by Sponsor. An imaging core lab charter will ensure that consistent policies and procedures are applied throughout the imaging core lab review and determination process, and will include a minimum of two core lab members. If an unresolvable disagreement is encountered, then a third member may be included or an alternative method may be used as needed.

For each enrolled subject, all images must be appropriately de-identified and submitted for core lab review. It is important that the images be saved in native DICOM format, and that all imaging sequences are sent (without pre-selecting specific frames). It is also important that the imaging sequences are captured chronologically and are clearly labeled with date and time stamps so that they can be correlated to pre-procedure, after recanalization, and post-procedure time points.

14 Statistical Methods and Sample Size

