7.2 Secondary Outcomes

The following secondary outcomes will be collected and evaluated in all enrolled patients:

- Carotid access time
 - Hospital arrival to neck incision
 - Neck incision to carotid exposure
 - Neck incision to carotid artery catheterization (includes securing of sheath)
 - Neck incision to femoral venous sheath access (includes securing of sheath)
 - Neck incision to initiation of reverse flow
- Time to final revascularization
 - Hospital arrival to OR
 - Last known well to final revascularization
 - Admission to final revascularization
 - OR to final revascularization
 - Cutdown to final revascularization
 - Arterial introduction of interventional tools to final revascularization
 - Total reverse flow time (CCA clamp to CCA unclamp)

- Device-related complications
- Neurologic assessment at 90 days (proportion of patients with a nondisabling or disabling stroke according to NIHSS)
- Technical success rate – Successful introduction of endovascular tools through the NOVIS Transcarotid NPS.
- Rates of revascularization success assessed by angiographic core lab (mTICI \geq 2b)

8 Study Population

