8.4 Exclusion Criteria

Each potential patient must be screened to ensure they do not meet any of the following exclusion criteria. This screening is based on known medical history and data available at the time of eligibility determination and enrollment.

1. Significant disease of the ipsilateral common carotid artery on routine CTA
2. Presence of a cervical ICA loop or other high-risk anatomical features of the ICA on routine CTA, that may preclude the use of the NOVIS NPS
3. Any active or recent hemorrhage within the past 30 days
4. Embolectomy contraindications
 - a. Pre-stroke mRS ≥ 2
 - b. NIHSS ≤ 5
 - c. ASPECTS ≤ 5
5. IV tPA has been or is being administered
6. Last known well > 24 hours ago
7. Known history of severe head injury within past 90 days with residual neurological deficit, as determined by medical history
8. Patient has an isolated hemisphere, defined as intracranial circulation that is fed only by the ipsilateral internal carotid artery and may be detected on prior CTA
9. Known history of neurological or psychiatric disease that would confound the neurological or functional evaluations, e.g., dementia with prescribed anti-cholinesterase inhibitor (e.g., Aricept)
10. Presumed septic embolus, suspicion of bacterial endocarditis or cerebral vasculitis
11. Known history of ipsilateral severe intracranial atherosclerotic disease ($\geq 70\%$ stenosis) documented on prior imaging
12. Patient is known to have an active COVID-19 infection
13. Female who is pregnant or lactating at time of admission
14. Current participation in another investigational drug or device study.
15. Evidence of any other disease or condition expected to compromise survival or ability to complete the endovascular procedure or follow-up assessments during the 90-day follow-up period (e.g. methamphetamine, cocaine, or other recreational drug use)
16. Patient has recurrent or metastatic malignancy or cancer
17. Known history of hemorrhagic diathesis or coagulation factor deficiency
18. Known risks for paradoxical embolism, including intracardiac right-to left shunt (e.g., PFO, ASD, VSD) or history of pulmonary embolism or deep vein thrombosis
19. Patients that have undergone a transradial or transbrachial mechanical thrombectomy attempt prior to enrollment

9 Patient Enrollment

A patient is considered enrolled after:

- 1) written informed consent is obtained,
- 2) meeting all inclusion and none of the exclusion criteria,
- 3) failed transfemoral therapy

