10.3.4 Endovascular Therapy

Patients will be treated with endovascular therapy system(s) (stentriever and/or aspiration catheters) currently cleared by the FDA, under their cleared indications for use, for thrombus removal in patients experiencing an acute ischemic stroke in the anterior circulation due to large vessel occlusion. Investigators will be trained to follow the published instructions for use for the endovascular therapy system used in the procedure. Deviations from the cleared time of usage must be documented as a protocol deviation. Ensure the neurointerventional devices are labeled with an outer diameter that is compatible with the inner diameter of the NOVIS NPS Arterial Sheath and attached rotating hemostasis valve.

These devices will be introduced into the vasculature via the NOVIS NPS Arterial Sheath, during this interventional step the NOVIS NPS will be set to High Flow and remain on this setting until the neurothrombectomy has been completed.

Once the endovascular therapy systems are introduced into the NOVIS NPS Arterial Sheath continuous reverse flow will be maintained throughout the interventional steps, until all other devices are removed and the thrombectomy attempt is complete.

The transcarotid intervention may be abandoned at the discretion of the treating operator. The operator will document reason for failure in patient records and study case report forms.

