10.3.5 Procedural Angiography

Angiographic evaluations will be performed pre-procedure, after recanalization, and post procedure to determine level of revascularization. Angiography must be performed in the involved territory.

Prior to the start of the procedure, the mTICI scores within the vascular territory being treated should be assessed. Angiographic films of the occlusion being treated must allow clear visualization of the target artery. The same orientation should be used before and after endovascular therapy in order to allow a valid analysis of the reperfusion status of the vessel(s). These angiographic evaluations will be submitted by the sites for core lab review.

In the event of a procedural complication or adverse event, detailed angiographic images should be obtained and submitted. All adverse events that occur during the procedure must be documented and recorded on the applicable CRFs.

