7.4. Summary of Revascularization Success

Revascularization Success is defined as an mTICI of ≥ 2 as assessed by the angiographic core lab. Results will be tabulated using counts and percentages and presented in Table 6.4.3 entitled *Summary of Revascularization Success*. Results will be supported by the data presented in Listing 6.4.3 titled *Angiographic Core Lab Adjudication of Postprocedural mTICI*, sorted by patient number and the date of procedure.

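### Revascularization success is scored on the post-procedure mTICI alone, with no reference to the grade left by the failed transfemoral attempt

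*Protocol*

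**What the plan says.** **Endpoint and threshold.** Protocol 7.2 lists "Rates of revascularization success assessed by angiographic core lab" with a threshold of mTICI 2b or better, and SAP Section 2 repeats that threshold. SAP 7.4 states something different: "Revascularization Success is defined as an mTICI of ≥ 2 as assessed by the angiographic core lab".

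**Time point.** Under Protocol 13.3 the core lab gives an "independent assessment of the secondary efficacy endpoint of mTICI reperfusion scores at post procedure". In SAP 7.4 the supporting Listing 6.4.3 is titled "Angiographic Core Lab Adjudication of Postprocedural mTICI".

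**What is collected.** Protocol 10.3.5 says: "Angiographic evaluations will be performed pre-procedure, after recanalization, and post procedure to determine level of revascularization". It adds: "Prior to the start of the procedure, the mTICI scores within the vascular territory being treated should be assessed". The films go to the core lab, and Protocol 13.3 requires time stamps that tie each sequence to one of the three time points.

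**Who is enrolled.** Protocol 10.3.2 and Appendix 4 allow two kinds of transfemoral failure: an unsuccessful thrombectomy attempt with at least 15 minutes elapsed since groin puncture, or anatomy that the operator judges to rule out the approach. Neither sets an upper limit on mTICI.

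**Abandoned cases and other routes.** Protocol 10.3.4: "The transcarotid intervention may be abandoned at the discretion of the treating operator". The reason must be recorded, but no scoring rule follows. Exclusion 19 in Protocol 8.4 covers "Patients that have undergone a transradial or transbrachial mechanical thrombectomy attempt prior to enrollment" and does not address what may happen later.

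**The concern.** NITE 1 is a single-arm study of salvage patients, many of whom may already have had a thrombectomy attempt on the same clot. A grade read once, at the end, describes the state of the vessel after everything that was done. It does not separate what the transcarotid treatment achieved from what was there when it began. With no control arm, the pre-NOVIS grade is the only within-study reference for making that separation.

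The stake is how the rate is interpreted. Protocol 23.5 names better reperfusion as a potential benefit of the approach, and SAP Section 2 foresees use of the results in regulatory submissions and manuscripts. Readers will take the rate as what the NOVIS route delivered.

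**Working it through.** The plan gives no target rate, power or sample-size formula for this endpoint, so there is no planned figure to reproduce. The check is a comparison of the text, followed by simple arithmetic.

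**Step 1. Can a patient count as a success with no change during NOVIS?** The mTICI definitions in Protocol Appendix 2 put 2a at under 50% filling of the territory and 2b at over 50%.

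| Grade before NOVIS | Grade after | Protocol 7.2 and SAP Section 2 (2b or better) | SAP 7.4 (2 or better) |
|---|---|---|---|
| 0 or 1 | 2b or 3 | success | success |
| 0 or 1 | 2a | not a success | success |
| 2a | 2a | not a success | success, no change |
| 2b | 2b | success, no change | success, no change |

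The third row needs only an attempt that partly reopened the vessel and was then called unsuccessful. The fourth needs a patient who already met the trial's own success grade and was still judged both occluded and a failed attempt.

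**Step 2. Do the analysis sets remove such patients?** No. The per-protocol set drops patients with major deviations, and the criteria listed in Protocol 22 and SAP Section 4 concern IRB approval, consent and falsified records. Enrollment (Protocol 9) is complete before NOVIS is placed, so abandoned cases stay in the ITT set and normally in the per-protocol set as well.

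**Step 3. Is the pre-NOVIS grade available?** Largely yes, under Protocol 10.3.5 and 13.3. What is unclear is its timing: the start of the procedure could mean before any thrombectomy, or after the last transfemoral pass and before NOVIS. Only the second serves this purpose.

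**Step 4. Size per patient.** With the denominator held at N, one reclassified patient moves the rate by 100/N points. N = 30 and 40 are the per-protocol minimum and maximum; 60 is the ITT maximum (Protocol 14.2).

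- 100/30 = 3.3
- 100/40 = 2.5
- 100/60 = 1.7

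**Step 5. Illustration.** Assume an attributable rate of 70% and one to three affected patients. Both are assumptions; the documents give neither.

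| N | Attributable | One added | Three added |
|---|---|---|---|
| 30 | 21/30 = 70.0% | 22/30 = 73.3% | 24/30 = 80.0% |
| 40 | 28/40 = 70.0% | 29/40 = 72.5% | 31/40 = 77.5% |
| 60 | 42/60 = 70.0% | 43/60 = 71.7% | 45/60 = 75.0% |

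The exact (Clopper-Pearson) 95% intervals at N = 30 are 50.6% to 85.3% for 21/30 and 61.4% to 92.3% for 24/30. They overlap widely, so three patients lie within sampling error. A misattribution of this kind, however, does not average out.

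**Step 6. Denominator.** The full step applies to a patient who starts and ends at 2a, and to an abandoned case, because both remain in the denominator as non-successes. If patients already at 2b or better are taken out of the denominator, the difference is smaller: for three of them at N = 30, 24/30 − 21/27 = 80.0% − 77.8% = 2.2 points.

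**The case against.** The best counter-argument is that the problem nearly disappears at the Protocol threshold. Inclusion criterion 2 requires an occlusion of the target segment, and Appendix 4 requires that a qualifying attempt was unsuccessful; a patient at 2b fits neither comfortably. This largely stands. No mTICI ceiling is written and the occlusion is not said to be re-confirmed after the passes, so the case is unlikely rather than excluded. Restoring 2b in SAP 7.4 would remove most of the exposure.

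Second, the reading may already be planned. SAP 5.2 has the core lab evaluate pre-operative and post-operative imaging, and detailed rules sit in a core lab charter that is not among the documents. This stands in part: the data exist, and what is missing is their use in the endpoint definition and tables.

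Third, the endpoint is secondary, carries no hypothesis test (Protocol 14.3) and has no comparator in SAP Table 1. This stands and sets the severity.

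Two stronger readings go too far. A reader might infer that every patient has had the clot treated already; the anatomical arm of the failure definition shows otherwise. A reader might also infer that reperfusion won by another route after abandonment is credited to NOVIS. No section provides for such a rescue, and Protocol 23.6 presumes that no other thrombectomy option remains. The post-procedure film may also naturally mean the end of the transcarotid procedure, which is the subject of Protocol 10.3. The documents are silent on how such a case is scored; they do not state a crediting rule. Counting technical success once tools have passed through the sheath simply follows its definition.

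**Conclusion.** The point holds in limited form. Success rests on the post-procedure grade alone, and followed as written the plan can count a patient who was already at the threshold before NOVIS. This concerns only patients who had a transfemoral attempt. It is plausible under SAP 7.4's threshold of 2 and unlikely at 2b. The scoring of abandoned cases, and of any later reperfusion by another route, is undefined.

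The size is 3.3, 2.5 or 1.7 points per affected patient at N = 30, 40 or 60, with the denominator held fixed. The number of such patients cannot be estimated from the documents, so no overall inflation should be claimed. This is a cheap improvement of low severity.

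**What to change.** 1. Reconcile SAP 7.4 with Protocol 7.2 and SAP Section 2, so that the threshold is mTICI 2b or better throughout.
2. State in Protocol 10.3.5 and 13.3 and in SAP 7.4 that the pre-procedure mTICI is the core-lab grade after the last transfemoral pass and before NOVIS. For patients enrolled on anatomy, use the last film before NOVIS.
3. Tabulate the shift from that grade to the grade at the end of treatment through the NOVIS sheath.
4. Report NOVIS-attributable success: below 2b before, 2b or better through the sheath. Count abandoned cases as non-successes. Show patients already at 2b or better in their own row rather than as failures, which would bias the rate downward, and state the denominator.
5. Keep final mTICI by any means as a separate line.
6. Apply the same end point, the end of treatment through the sheath, to the intervals to final revascularization in Protocol 7.2.

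These are scoring rules only; they leave the operator's decisions as they are. The cost is one more read of films already submitted, wording in the Protocol (through its amendment process), SAP and core lab charter, and a possibly lower reported rate.

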14.1 Populations for Analysis

The Intent-to-Treat (ITT) population is defined as patients who are enrolled as discussed in Section 9 who have consented (only once prior to screening), who meet all inclusion and none of the exclusion criteria , and in whom transfemoral therapy has been deemed a failure.

The per protocol (PP) population will be comprised of patients from the ITT population AND for whom no major protocol deviations have occurred.

14.2 Sample Size

A minimum of 30 and a maximum of 40 patients will be enrolled into the PP population and analyzed in this study. Enrollment in the ITT cohort will cease when 30 PP patients have been accrued. Additional patients beyond 30 who are successfully enrolled while waiting for the 30th PP patient to complete the 90-day follow-up period, will be analyzed in the cohort for which they qualify, whether PP or ITT. Enrollment will continue till a maximum of 60 patients are enrolled in the ITT population or the DSMB stops the study for safety reasons.

14.3 Endpoint Analyses and Hypothesis Testing

No formal statistical hypothesis will be tested because this is a feasibility study with a small sample size. Serious Adverse Events will be tabulated and reported accordingly.

The primary endpoint and all secondary endpoints will be analyzed based on both the ITT and PP population. All available data on the ITT patients who enrolled in the study will be included.

15 Data Collection

Data will be entered into a validated electronic data management system using standardized electronic Case Report Forms (eCRFs). All efforts should be made by the Investigator and trained study staff to complete the eCRFs in their entirety. This includes all data regarding adverse events, protocol deviations, patients lost to follow-up, and other relevant data.

15.1 Required Data

For the duration of the study, the Investigator will maintain complete and accurate documentation, including but not limited to, medical records, study progress notes, laboratory reports, CRFs, signed patient informed consent forms, device accountability logs, correspondence with the reviewing IRB, sponsor and Study Monitor, adverse event reports, and information regarding patient discontinuation or completion of the study.

The Investigator/institution will permit direct access to source data and documents for study-related monitoring, audits, IRB reviews, event adjudication and regulatory inspections to be performed. The Investigator will obtain, as part of the informed consent process, permission for authorized sponsor employees, study monitors or regulatory authorities to review, in confidence, any medical records that concern patients in this trial, whether or not they contain personally identifying information.

